9.7 SMWQ

Medication withdrawal symptoms assessed by SMWQ total scores at the scheduled visits during the double-blind treatment period and follow-up period will be summarized for the Safety Sample by treatment group and overall. The number of patients, mean, median, range and standard deviation will be presented.

SAP 405-201-00013

9.8 Medication Handling Irregularities (MHIs) and Events Subject to Additional Monitoring (ESAMs)

MHIs and ESAMs will be summarized for the Safety Sample by treatment group and overall. By-patient listings will be provided.

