3.7.1.6 Visit 15 (Follow-up)

Subjects who terminate early, decide to not enroll in Trial 405-201-00015, or who are not eligible to enroll in Trial 405-201-00015, will be required to participate in an additional follow-up via telephone call 10 days after the last dose of IMP. For subjects who early terminate or decline participation in the open-label trial, they will be instructed to refrain from utilizing prohibited concomitant medications (Section 4.1), including ADHD treatments, until after the follow-up telephone call 10 days after the last dose of IMP. The assessments described in the Follow-up Schedule of Assessments (Table 3.7-2) will be completed.

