7.5.5 Other Safety Data

Medication withdrawal symptoms assessed by SMWQ total scores at the scheduled visit(s) will be summarized by treatment group by descriptive statistics. Details will be described in the SAP.

Suicidality monitored during the trial using the C-SSRS will be summarized by treatment group by descriptive statistics. Details will be described in the SAP.

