10.3.6 Study Medication Withdrawal Questionnaire (SMWQ)

The SMWQ is a questionnaire to assess withdrawal symptoms. The SMWQ is a modification of the Amphetamine Withdrawal Questionnaire in which the terms “amphetamines and methamphetamine” are replaced with the term “the study medication.” The SMWQ is assessed at Day 35 and Day 42/ET in the double-blind treatment period and at 1, 2, 3, 5, 7, and 10 days after the last dose of IMP in the follow-up period.

SAP 405-201-00013

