- CT-14.1.3 Columbia-Suicide Severity Rating Scale(C-SSRS) During the Double-Blind Treatment Period, Suicidal Ideation by Type (Safety Sample)
- CT-14.1.4 Columbia-Suicide Severity Rating Scale(C-SSRS) During the Double-Blind Treatment Period, Treatment Emergent Suicidal Behavior and Ideation (Safety Sample)
- CT-14.1.5 Columbia-Suicide Severity Rating Scale (C-SSRS) – Listing of Treatment Emergent Suicidal Ideation During the Double-Blind Treatment Period (Safety Sample)

SAP 405-201-00013

- CT-14.1.6 Columbia-Suicide Severity Rating Scale (C-SSRS) – Listing of Treatment Emergent Suicidal Behavior During the Double-Blind Treatment Period (Safety Sample)
- CT-14.1.7 Columbia-Suicide Severity Rating Scale (C-SSRS) – Listing of Treatment Emergent Serious Suicidal Ideation During the Double-Blind Treatment Period (Safety Sample)
- CT-14.1.8 Columbia-Suicide Severity Rating Scale (C-SSRS) – Listing of Worsening Suicidal Ideation During the Double-Blind Treatment Period (Safety Sample)
- CT-14.2.1 Columbia-Suicide Severity Rating Scale (C-SSRS) During the Single-Blind Placebo Run-in Period, Suicidality (Safety Sample)
- CT-14.2.2 Columbia-Suicide Severity Rating Scale (C-SSRS) During the Single-Blind Placebo Run-in Period, Suicidal Behavior by Type (Safety Sample)
- CT-14.2.3 Columbia-Suicide Severity Rating Scale (C-SSRS) During the Single-Blind Placebo Run-in Period, Suicidal Ideation by Type (Safety Sample)
- CT-14.2.4 Columbia-Suicide Severity Rating Scale (C-SSRS) During the Single-Blind Placebo Run-in Period, Treatment Emergent Suicidal Behavior and Ideation (Safety Sample)
- CT-14.2.5 Columbia-Suicide Severity Rating Scale (C-SSRS) – Listing of Treatment Emergent Suicidal Ideation During the Single-Blind Placebo Run-in Period (Safety Sample)
- CT-14.2.6 Columbia-Suicide Severity Rating Scale (C-SSRS) – Listing of Treatment Emergent Suicidal Behavior During the Single-Blind Placebo Run-in Period (Safety Sample)
- CT-14.2.7 Columbia-Suicide Severity Rating Scale (C-SSRS) – Listing of Treatment Emergent Serious Suicidal Ideation During the Single-Blind Placebo Run-in Period (Safety Sample)
- CT-14.2.8 Columbia-Suicide Severity Rating Scale (C-SSRS) – Listing of Worsening Suicidal Ideation During the Single-Blind Placebo Run-in Period (Safety Sample)
- CT-15 Summary of Mean Study Medication Withdrawal Questionnaire (SMWQ) Total Score During the Double-Blind Treatment Period and Follow-up Period by Study Day (Safety Sample)

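### SMWQ withdrawal scores are summarised visit by visit with no within-subject change from the last on-drug score, and the Day 10 mean comes from a selected subset that is not comparable with earlier means

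*SAP*

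**What the plan says.** Protocol 7.5.5 says that "SMWQ total scores at the scheduled visit(s) will be summarized by treatment group by descriptive statistics" and leaves the details to the SAP. SAP 9.7 covers treatment and follow-up, by arm and overall, on the Safety Sample: "Medication withdrawal symptoms assessed by SMWQ total scores at the scheduled visits during the double-blind treatment period and follow-up period will be summarized", and "The number of patients, mean, median, range and standard deviation will be presented". The only SMWQ table in SAP Section 13 is CT-15, titled "Summary of Mean Study Medication Withdrawal Questionnaire (SMWQ) Total Score During the Double-Blind Treatment Period and Follow-up Period by Study Day".

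SAP 10.3.6 puts the questionnaire "at Day 35 and Day 42/ET in the double-blind treatment period and at 1, 2, 3, 5, 7, and 10 days" after the last dose. The schedule of assessments (Protocol Table 3.7-1) has no SMWQ before Day 35, so there is no pre-treatment score.

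Who is due at each contact differs:

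- **Days 1, 2, 3, 5 and 7:** Protocol 3.7.1.5 requires these of every subject, completer or not.
- **Day 42/ET:** Protocol 3.7.1.4.2 has early terminators complete the Day 42 procedures at their termination visit.
- **Day 10:** Protocol 3.7.1.6 limits this call. "Subjects who terminate early, decide to not enroll in Trial 405-201-00015, or who are not eligible to enroll in Trial 405-201-00015" are the ones who "will be required to participate in an additional follow-up via telephone call 10 days after the last dose of IMP".

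**The concern.** A withdrawal effect shows as a rise in the same person once drug is stopped. With no pre-treatment SMWQ, the last on-drug score is the only personal reference, and the SAP never uses it. Elsewhere the SAP does work within subjects: it plans change from baseline for laboratory tests (9.2), vital signs (9.3) and body weight (9.5.1), and it defines worsening relative to baseline for the C-SSRS (9.6).

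Two things follow. First, per-visit summaries cannot show how many people rose or by how much, so a minority with a marked rise can sit behind a flat mean. Second, CT-15 runs from Day 35 through Day 10 of follow-up as one sequence by study day. The last entry belongs to a group selected after randomization. A step up or down at Day 10 could reflect who was still being called rather than what happened after stopping.

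**Working it through.** The documents give no SMWQ figure, scale range or SD, so there is no stated result to reproduce. Two things can be checked: what a per-visit table can and cannot show, and how the make-up of the Day 10 group changes.

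**Per-visit against paired statistics.** If the same people are scored at both times, the difference between two visit means equals the mean within-subject change, so the mean itself is not lost on Days 1 to 7. The spread is lost. The variance of the change is s₁² + s₂² − 2ρs₁s₂, and ρ, the correlation between a person's two scores, cannot be recovered from the visit SDs. Nor can the largest individual rise.

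**Inputs for Day 10.**

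- Planned randomized: 450 (Protocol 3.3.1).
- Planned completers: 292 (Protocol 3.3.1).
- Early terminators, E: 450 − 292 = 158, taking every non-completer as an early terminator who stays in follow-up.
- Share of completers who enter the rollover trial, r: not in the documents, so varied from 0% to 100%.

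**Formulas.** Subjects due at Day 10: n₁₀ = 158 + 292(1 − r). Early-terminator share at Day 10: 158 / n₁₀. At Day 42/ET and on Days 1 to 7 the scheduled share is 158 / 450 = 35.1%.

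Suppose early terminators and completers differ by d at all times and nobody changes after stopping. The Day 10 mean then differs from the Day 42/ET mean by d × (share at Day 10 − 0.351). The last column uses an assumed d of 0.5 SD.

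| Rollover r (assumed) | n₁₀ | Early-terminator share at Day 10 | Shift at d = 0.5 SD |
|---|---|---|---|
| 0% | 450 | 35% | 0.00 SD |
| 25% | 158 + 219 = 377 | 42% | 0.03 SD |
| 50% | 158 + 146 = 304 | 52% | 0.08 SD |
| 80% | 158 + 58.4 = 216 | 73% | 0.19 SD |
| 100% | 158 | 100% | 0.32 SD |

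For example, at 80%: 158 / 216.4 = 0.730, and 0.5 × (0.730 − 0.351) = 0.19 SD. The shift is proportional to d, so it is zero if d is zero, and its sign is that of d. The documents do not say whether early terminators score higher or lower.

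**Days 1 to 7.** The subjects due are the same as at Day 42/ET, so the scheduled shift in composition is zero.

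**Day 35.** Anyone who stopped earlier has no Day 35 score, so Day 42/ET is the reference that matches follow-up. That entry has its own weakness: it pools Day 42 scores with termination-visit scores, and a termination visit may fall after the last dose.

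**The case against.** The strongest defence is that five of the six follow-up contacts are free of the composition problem by design. Days 1, 2, 3, 5 and 7 are due in everyone, and early terminators also contribute to Day 42/ET. A reader might infer that all on-drug and off-drug means compare different people. The documents do not support that: among the follow-up contacts it holds by design only at Day 10. On the earlier days it would need actual missed contacts, and no SMWQ completion figures are given.

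The table will also show n, so the fall at Day 10 will be visible. That stands, but n does not say who is missing and gives no within-person change.

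The placebo arm has the same Day 10 rule, so a comparison with placebo removes the shift to the extent that selection is alike in the arms. A reader might go further and infer that it is unlike, because the output appended to the SAP shows 38 of 147 (26%), 28 of 147 (19%) and 25 of 144 (17%) subjects without a Day 42 AISRS on 200 mg, 400 mg and placebo. Those figures do not establish an imbalance in the Day 10 SMWQ set. They count AISRS ratings outside an analysis window (SAP 10.1), which is neither early termination nor SMWQ missingness. SMWQ is not among the scales that SAP 10.1 lists for windowing. The Day 10 set also contains completers who do not roll over, whose numbers by arm are unknown.

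Finally, SMWQ is a descriptive safety summary with no test attached, and SAP 9.1.1 tabulates adverse events up to 30 days after dosing. That limits the consequence but does not make the Day 10 mean comparable.

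**Conclusion.** The point holds in a limited form. No within-subject SMWQ change is planned at any follow-up day, although the scores for it are collected. The Day 10 mean is not comparable with the Day 42/ET mean or the Day 1 to 7 means, because the Day 10 call covers a subset defined by events after randomization.

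The size cannot be fixed from the documents. On planned numbers, the early-terminator share rises from 35% to between 52% and 100% for rollover between 50% and 100%. With an assumed 0.5 SD difference between early terminators and completers, that moves the Day 10 mean by 0.08 to 0.32 SD with no withdrawal at all. At 0% rollover nothing moves. It would be tempting to state a bias in SMWQ points, or a bias in the drug-placebo contrast. Neither is supported, because the scale's range and SD, the rollover rate and the make-up of the Day 10 group by arm are all absent.

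No efficacy conclusion is affected. This is a cheap improvement to one safety table.

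**What to change.** Add one panel to CT-15, by treatment arm:

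- Change from each subject's last SMWQ taken on or before the last dose to each of Days 1, 2, 3, 5 and 7, in subjects with both scores, with n, mean, median, range and SD.
- The largest rise per subject over Days 1 to 7, summarised the same way and read against placebo.
- The number of subjects with no on-drug score. SMWQ starts at Day 35, so someone who stopped earlier and had the termination visit after the last dose has none.
- Day 10 in its own block, split into completers and early terminators, with paired change where both scores exist. It should not be displayed as the next point after Day 7. Pairing removes between-person differences but still leaves Day 10 a selected group, so the split is needed as well.

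The cost is one panel in an existing table, from data already collected. The downside is that some early terminators cannot be paired, which is why their number has to be reported.

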9.9 Concomitant Medications

Number and proportion of patients taking concomitant medications prior to the single-blind placebo run-in period, during the single-blind placebo run-in period, during the double-blind treatment period, and after study therapy are tabulated by drug classification using the World Health Organization (WHO) drug dictionary. For the double-blind treatment period Randomized Sample, data will be presented by treatment group and overall.

9.10 Extent of Exposure

The start date of double-blind IMP - centanafadine or placebo - will be the first day of double-blind dosing. The number and percentage of subjects who receive double-blind IMP, will be presented by week and by treatment group. Each dosing week will be based on the actual week; i.e., Day 1-7 in Week 1, Day 8-14 in Week 2, etc. This summary will be performed on the Safety Sample.

The mean daily dosage will be summarized by week and treatment group using descriptive statistics. The mean daily dosage per subject per week will be determined for each week of the study. This will be calculated by dividing the sum of individual total doses by the number of days in the week interval. The summary will contain for each treatment group the number of patients receiving double-blind IMP, and the mean and range of the mean daily dose for each week.

10 Conventions

10.1 Study Visit Windows

Study visit windows will be used to map visits using study day intervals. This visit window convention applies to tables and listings for all efficacy and safety scales (AISRS, CGI-S, AIM-A, ASRS and CGI Change from Baseline). This derived study window variable will be named as DAY and will be footnoted. In listings it will be listed along with the eCRF study visit.

[Table 10-1](#) shows classifications for study day intervals in the double-blind treatment period. The variable “target day” is defined using the number of days since the start of double-blind

SAP 405-201-00013

dosing in the double-blind treatment period. The first day of double-blind dosing is defined as “Day 1”.

If more than one observation falls within a particular study day interval, then the last observation within that interval is used. Evaluations occurring more than three days after the last double-blind dosing date and evaluations occurring during the follow-up period will not be mapped into study visit windows and will be excluded from the double-blind treatment period analysis.

Table 10-1: Study Day and Visit Windows in the Double-Blind Treatment Period

Day	Target Day ^a	Study Day Interval ^a
7	7	2-10
14	14	11-17
21	21	18-24
28	28	25-31
35	35	32-38
42	42	39-49 ^b

^a Relative to the first day of double-blind IMP in the double-blind treatment period.

^b Evaluations occurring more than three days after the last double-blind dosing date and evaluations occurring during the follow-up period will be excluded from the double-blind treatment period analyses.

10.2 Pooling of small centers

Primary efficacy analysis will be performed on the Efficacy Sample which comprises those subjects in the Randomized Sample who have a baseline value for the double-blind treatment period and at least one post-randomization value for AISRS total score in the double-blind treatment period. Small centers will be defined as centers that do not have at least one evaluable subject (evaluable with regard to the primary efficacy variable) in each treatment arm in the double-blind treatment period. All small centers will be pooled to form “pseudo centers” for the purpose of analysis according to the following algorithm. Small centers will be ordered from the largest to the smallest based on the number of evaluable subjects (i.e., subjects who have a baseline value for the double-blind treatment period value and at least one post-randomization value for AISRS total score in the double-blind treatment period). The process will start by pooling the largest of the small centers with the smallest of the small centers until a non-small center is formed. This process will be repeated using the centers left out of the previous pass. In case of ties in center size, the center with the smallest center code will be selected. If any centers are left out at the end of this process, they will be pooled with

SAP 405-201-00013

the smallest pseudo centers, or if no pseudo centers exist, they will be pooled with the smallest non-small center.

10.3 Scales: Rules for Scoring and Handling of Missing Data

10.3.1 Adult ADHD Investigator Symptom Rating Scale (AISRS)

The AISRS is utilized as the primary efficacy assessment of a subject's level of ADHD symptoms. It is a modified version of the ADHD Rating Scale that reflects the impact and severity of ADHD among adults and will be administered at each scheduled visit in the screening period, the single-blind placebo run-in period, the double-blind treatment period, and at 2 and 7 days after the last dose of IMP in the follow-up period. It is a clinician-administered scale that measures the 18 symptoms of adult ADHD using a Likert scale: 0 (none); 1 (mild); 2 (moderate); and 3 (severe) and uses a semi-structured interview methodology with suggested prompts for each item to improve interrater reliability. The scale's 18 items directly correspond to the 18 DSM-5 symptoms of ADHD where 9 inattentive items alternate with 9 hyperactive impulsive items. The maximum total score for the scale is 54 points, with 27 points for each subscale. The total score is the sum of both the Inattentive and Hyperactive Impulsive subscales.

The AISRS inattentive subscale score and hyperactive-impulsive subscale score, as well as the AISRS total score is set to be missing if more than one item of a subscale is missing for inattentive subscale or hyperactive-impulsive subscale, separately. If one item is missing for a given subscale (inattentive or hyperactive-impulsive), then the subscale score is derived as the mean of scores from the 8 non-missing items multiplied by 9. All imputed scores are rounded to the first decimal place. The 9 inattentive items consist of the 9 odd numbered items and the 9 hyperactive impulsive items consist of the 9 even numbered items.

10.3.2 Clinical Global Impression Severity of Illness Scale – Modified for Attention-Deficit Hyperactivity Disorder

The CGI-S modified is an observer-rated scale that will be used to measure symptom severity. To perform this assessment, the investigator or rater will respond to the following question: "Considering your total clinical experience with adult ADHD, how mentally ill is the patient at this time?" Response choices include: 1 = normal, not at all ill; 2 = borderline mentally ill; 3 = mildly ill; 4 = moderately ill; 5 = markedly ill; 6 = severely ill; and 7 = among the most extremely ill patients. CGI-S is assessed at each scheduled visit in the double-blind treatment period.

SAP 405-201-00013

10.3.3 Clinical Global Impression Change from Baseline

The CGI Change from Baseline is an observer-rated scale that will be used to measure the subject's total improvement compared to before trial drug treatment was initiated. The rater or investigator will rate the subject's total improvement relative to baseline. Response choices include: 1 = very much improved, 2 = much improved, 3 = minimally improved, 4 = no change, 5 = minimally worse, 6 = much worse, and 7 = very much worse. CGI Change from Baseline is assessed at each scheduled visit in the double-blind treatment period except for the Day -1 visit.

10.3.4 Attention-Deficit Hyperactivity Disorder Impact Module – Adult (AIM-A)

The AIM-A is a subject self-report questionnaire which assesses quality of life in adults with ADHD. The questionnaire has 4 global quality of life items, 5 economic impact items, and 5 multi-item scales that assess the following key concepts: Living with ADHD, General Well-Being, Work, Home and School Performance and Daily Functioning. Additionally, Relationships and Communication, and Impact of Symptoms are also included.

10.3.5 Adult ADHD Self Report Scale (ASRS)

The ASRS is a self-report questionnaire developed by the WHO. The subject will answer 18 questions about the frequency of recent ADHD symptoms that are consistent with the DSM-IV criteria. The ASRS is assessed at the scheduled visits during the screening period, the single-blind placebo run-in period, and at Days -1, 28 and 42/ET during the double-blind treatment period.

The total score of (18 item) ADHD Symptoms score of the ASRS is set to be missing if more than one item of a subscale is missing for inattentive subscale or hyperactive-impulsive subscale, separately. If one item is missing for a given subscale (inattentive or hyperactive-impulsive), then the subscale score is derived as the mean of scores from the 8 non-missing items multiplied by 9. All imputed scores are rounded to the first decimal place. The 9 inattentive items consist of items 1-4 and 7-11 and the 9 hyperactive impulsive items consist of items 5-6 and 12-18.

10.3.6 Study Medication Withdrawal Questionnaire (SMWQ)

The SMWQ is a questionnaire to assess withdrawal symptoms. The SMWQ is a modification of the Amphetamine Withdrawal Questionnaire in which the terms “amphetamines and methamphetamine” are replaced with the term “the study medication.” The SMWQ is assessed at Day 35 and Day 42/ET in the double-blind treatment period and at 1, 2, 3, 5, 7, and 10 days after the last dose of IMP in the follow-up period.

SAP 405-201-00013

10.3.7 Columbia-Suicide Severity Rating Scale (C-SSRS)

Suicidality will be monitored during the trial using the C-SSRS. The C-SSRS is a semi-structured interview that captures the occurrence, severity, and frequency of suicide-related thoughts and behaviors during the assessment period. The interview includes definitions and suggested questions to solicit the type of information needed to determine if a suicide-related thought or behavior has occurred. The interview and rating for the C-SSRS must be completed by a licensed clinician who has been successfully trained to rate this scale by the sponsor or a designee and is medically responsible for the subject. Documentation of trial training should be maintained in the investigational site's files.

The C-SSRS has a "Screening/Baseline" version, which will be completed at screening and a "Since Last Visit" version that will be completed at all other visits (including the ET visit, if applicable). There are a maximum of 19 items to be completed: 7 required, 10 potential additional items if there is a positive response to a required item, and 2 items for suicide/suicide behavior present during the interview. The C-SSRS uses dichotomous scales (i.e., yes or no), Likert scales, and text or narrative to further describe the thoughts or behaviors.

The C-SSRS is assessed at each scheduled visit in the screening period, the single-blind placebo run-in period, the double-blind treatment period, and at 2 and 7 days after the last dose of IMP in the follow-up period.

SAP 405-201-00013

11 References

- ¹ Siddiqui O, Hung JHM, O'Neill R. MMRM vs. LOCF: A comprehensive comparison based on simulation study and 25 NDA datasets. *J Biopharmaceutical Stats.* 2009; 19(2):227-46.
- ² Diggle P, Kenward MG. Informative drop-out in longitudinal data analysis. *Applied Statistics.* 1994; 43:49-93.
- ³ Little RJA. Pattern-mixture models for multivariate incomplete data. *J Am Stat Assoc.* 1993; 88:125-34.
- ⁴ Little RJA. Modeling the drop-out mechanism in repeated measures studies. *J Am Stat Assoc.* 1995; 90:1112-21.
- ⁵ Hedeker D, Gibbons RD. Application of random effects pattern-mixture models for missing data in longitudinal studies. *Psychological Methods.* 1997; 2:64-78.
- ⁶ Ali MW, Siddiqui O. Multiple imputation compared with some information dropout procedures in the estimation and comparison of rates of change in longitudinal clinical trials with dropouts. *J Biopharmaceutical Stats.* 2000;10(2):165-81.
